5.1 THERAPEUTIC/DIAGNOSTIC AGENTS

5.2 3F8 monoclonal antibody (IND number of BB-IND-8449)

5.2.1 Source and Pharmacology: Monoclonal antibody 3F8 is purified by column chromatography. The final product is tested to assure that it is free of nucleic acid, murine viruses, bacteria, fungi, mycoplasma and pyrogens. Plasma concentrations achieved after a 5 mg/m² and 20 mg/m² IV dose were 1.1 +/- 0.6 and 3.7 +/- 1.4 ug/mL, respectively. Supplier: 3F8 is manufactured as an investigational agent.

5.2.2 Formulation and Stability: The purified antibody is frozen at -80°C, at 2 mg/mL 0.1 M citrate-phosphate pH 4.2 buffer in glass vials. At -80°C it is stable for at least 3 years. For IV administration, 3F8 should be diluted into 10 ml 5% human serum albumin and millipore (0.2 um) filtered before use. Route of Administration: IV infusion.

5.3 Yeast-derived human recombinant granulocyte-macrophage colony stimulating factor (GM-CSF; LEUKINE (sargramostim)) is produced by Berlex Laboratories, Seattle, WA.

5.3.1 LEUKINE is a sterile, white, preservative-free, lyophilized powder suitable for IV infusion upon reconstitution of 250 mcg vials; these vials should be reconstituted aseptically with 1.0 ml Sterile Water for Injection, USP (without preservative). The reconstituted LEUKINE solutions are clear, colorless, isotonic with a pH of 7.4 ± 0.3, and contain 250 mcg/ml of Sargramostim. The single-use vial should not be re-entered or reused. Do not save any unused portion for later administration. Vials containing 500 mcg of LEUKINE are already in solution and are multiple dose vials.

5.3.2 During reconstitution the Sterile Water for Injection, USP should be directed at the side of the vial and the contents gently swirled to avoid foaming during dissolution. Avoid excessive or rigorous agitation; do not shake.

5.3.3 Dilution for IV infusion should be performed in 0.9% Sodium Chloride Injection, USP. If the final concentration of LEUKINE is below 10 mcg/ml, Albumin (Human), add 1 mg Albumin (Human) per 1 ml 0.9% Sodium Chloride Injection, USP (e.g. use 1 ml 5% Albumin [Human] in 50 ml 0.9% Sodium Chloride Injection, USP).

5.3.4 An in-line membrane filter is not to be used for IV infusion of LEUKINE.

5.3.5 LEUKINE contains no antibacterial preservative and therefore should be administered as soon as possible, and within 6 hours following reconstitution and/or dilution for IV infusion. Store LEUKINE powder, reconstituted solutions, or diluted solutions under refrigeration at 2-8°C (36-46°F); do not freeze or shake. LEUKINE vials are intended for single

use only; discard any unused solution after 6 hours. Do not use beyond the expiration date printed on the vial.

5.3.6 In the absence of compatibility and stability information, no other medication should be added to infusion solutions containing LEUKINE. Use only 0.9% Sodium Chloride Injection, USP to prepare IV infusion solutions.

5.3.7 Aseptic technique should be employed in the preparation of all LEUKINE Solutions. To assure correct concentration following reconstitution, care should be exercised to eliminate any air bubbles from the needle hub of the syringe used to prepare the diluent. Parenteral products should be inspected visually for particulate matter and discoloration prior to administration whenever solution and container permit.

5.3 13-cis-Retinoic Acid (NDC #0004-0155-01,0004-0169, 0004-0156-01-ISOTRETINOIN, ACCUTANE)

5.3.1 Source and Pharmacology: The exact mechanism of retinoic acid (RA)-induced maturation of tumor cells is not known. In neuroblastoma cell lines it has been shown to down regulate MYCN RNA and protein expression, and such down regulation correlates with the ability of isotretinoin to induce tumor cell growth arrest. Recent studies using gene transfection directly implicate down regulation of MYCN expression by isotretinoin as a key event in achieving sustained arrest of neuroblastoma cell proliferation. RA also appears to enhance normal hematopoietic differentiation by increasing the responsiveness of myeloid and erythroid progenitor cells to the action of myeloid colony stimulating activity and erythropoietin, respectively. Metabolism: RA is 99.9% bound in plasma (almost entirely to albumin) and has a half-life of 10-20 hours. The major metabolite is 4-oxoisotretinoin, and excretion is in the urine and feces. A single oral dose of 100mg/m² isotretinoin will produce peak plasma levels of 1-2mM. The mean peaktime is 3.2 hours after 80mg orally, with a terminal t_{1/2} of 10 to 20 hours. Administering 160 mg/m²/day to children after autologous bone marrow transplantation has been shown to achieve 13-cis-RA levels of 5 to 7 micromolar.

5.3.2 Formulation and Stability: Isotretinoin, which is the 13-cis isomer of retinoic acid, will be used. This is a yellow-orange crystalline powder with a molecular weight of 300.44. Isotretinoin is sensitive to light and oxygen, and so it should not be removed from the capsule for longer than one hour prior to administration to the patient and it should be kept in subdued light as much as possible.

5.3.3 Guidelines for Administration: PO with fat-containing food or milk to enhance absorption. Administration of the entire capsule is to be encouraged and small children can be trained to swallow them using similar sized candy.

5.3.4 Supplier: Isotretinoin is available commercially under the trade name ACCUTANE (Roche Laboratories) in 10mg, 20mg, and 40mg soft gelatin capsules. See package insert for further information.

6.1 CRITERIA FOR SUBJECT ELIGIBILITY

Patients must have neuroblastoma. They can have evaluable (bone marrow [+]) by

Amended: 04/24/12

Page 15 of 34

histology, abnormal MIBG or PET scan consistent with bone marrow involvement), but not progressive, disease (**Group 1**). Patients in complete/very good partial remission (CR/VGPR; no evaluable or measurable disease) yet at high risk for relapse are also eligible (**Group 2**).

6.2 Subject Inclusion Criteria

- Diagnosis of neuroblastoma as defined by international criteria,⁹¹ i.e., histopathology (confirmed by the MSKCC Department of Pathology) or bone marrow metastases plus high urine catecholamine levels.
- Neuroblastoma, as defined by risk-related treatment guidelines and the International Neuroblastoma Staging System, i.e., stage 4 with (any age) or without (>18 months) MYCN-amplification,^{93a} or MYCN-amplified neuroblastoma other than stage 1.^{93b,93c}
- Group 1 patients have neuroblastoma (as defined above) resistant to standard therapy, as evidenced by incomplete response in bone marrow, but no MIBG-avid soft tissue tumor and no progressive disease.
- Group 2 patients have no evidence of disease, i.e., are in CR/VGPR from neuroblastoma (as defined above).
- Signed informed consent indicating awareness of the investigational nature of this program.

6.3 Subject Exclusion Criteria

- Existing severe major organ dysfunction, i.e., renal, cardiac, hepatic, neurologic, pulmonary, or gastrointestinal toxicity \geq grade 3.
- Progressive disease or MIBG-avid soft tissue tumor.
- History of allergy to mouse proteins.
- Active life-threatening infection.
- Human anti-mouse antibody (HAMA) titer >1000 Elisa units/ml.
- Inability to comply with protocol requirements.

7.0 RECRUITMENT PLAN

In each of the past 2 yrs, 23 patients have been treated on the predecessor of this protocol. We anticipate an increase in this accrual rate, which will allow rapid realization of preliminary conclusions, with completion of the trial in ~3 yrs. Given the favorable prior efficacy-toxicity profile with 3F8/GM-CSF, we expect that all patients will complete the trial. Patients will be offered participation in this study by their attending physician in the Department of Pediatrics, Memorial Sloan-Kettering Cancer Center. No patient will be identified by chart review or direct advertising. The attending physician will be responsible for explaining the study, obtaining written informed consent, and registering the patient on study. Patients will mainly be children

and adolescents because of the nature of neuroblastoma (90% of patients are <6 years old at diagnosis). Patients of both sexes and all ethnic backgrounds are eligible for this study.

8.1 PRETREATMENT EVALUATION (TABLE 4)

8.2 Complete history and physical examination.

8.3 Complete blood count, serum creatinine, blood urea nitrogen, serum aspartate aminotransferase, serum alanine aminotransferase, and serum total bilirubin

8.4 Echocardiogram.

8.5 Urine catecholamine levels.

8.6 Bone marrow aspirates from bilateral anterior and bilateral posterior iliac crests, and biopsies from any two separate sites. The specimens are studied by:

- Standard histochemical methods for the presence of tumor cells.
- Immunocytology using a panel of monoclonal antibodies that react with antigens associated with neuroblastoma ([name], Research Lab).

8.7 CT or MRI of primary tumor site, plus other specific or suspected sites of tumor.

8.8 Scintigraphic studies (^{99m}Tc-MDP-bone scan or MIBG scan⁹² or PET scan.⁹³).

9.1 TREATMENT/INTERVENTION PLAN

9.2 **Schedule:** The total dosage of 3F8 per cycle is the same as in prior trials (100 mg/m²), administered at 20 mg/m²/day and infused over ~1.5 hr or less (0.5 hr is customary), with analgesics and antihistamines used as needed for expected side-effects. 3F8 is started ~1 hr after completion of GM-CSF administration. GM-CSF is dosed at 250 mcg/m²/day from day -5 to day +1 (Wednesday to Tuesday is customary), and is 500 mcg/m²/day thereafter (i.e., on days +2 to +4; Wednesday to Friday), as in the predecessor protocol.^{18,74} Patients come off study if progressive disease occurs or if there is life-threatening grade 4 toxicity from 3F8; otherwise, patients will receive a minimum of 4 cycles of treatment and will continue treatment through 24 months. It is expected that patients will receive ~10 cycles.

For **Group 1** patients (enrolled on study for treatment of primary refractory disease), the break between end of a cycle of 3F8/GM-CSF and start of next cycle is 2-to-4-weeks through 4 cycles after achievement of CR in BM; subsequent breaks are ~8 weeks. In this group, isotretinoin is started after documentation of response to, and after ≥2 cycles of, 3F8/GM-CSF. Road map/schema is in section 4.2.

For **Group 2** patients (enrolled on study in CR/VGPR, i.e., with no evidence of disease), the break between end of a cycle and start of next cycle is 2-to-4 weeks through 4 cycles;

subsequent breaks are ~8 weeks. Isotretinoin is started after cycle 2 of 3F8/GM-CSF. Road map/schema is in section 4.2. Regarding patients in second or greater CR from relapse in the central nervous system, if they develop early HAMA which precludes timely completion of the minimum of 4 cycles of 3F8/GM-CSF, they are eligible to go off protocol, to be treated with low-dose maintenance regimens of irinotecan,⁹⁴ temozolomide,⁹⁵ or the two agents combined;⁹⁶ they can resume treatment with 3F8/GM-CSF if HAMA becomes negative.

Patients who develop early HAMA which precludes timely treatments with 3F8/GM-CSF (>4 week delay) are eligible to receive low-dose maintenance regimens such as irinotecan alone,⁹⁴ temozolomide alone,⁹⁵ irinotecan-temozolomide,⁹⁶ or cyclophosphamide-topotecan.⁹⁷ They can also receive anti-HAMA agents such as rituximab and cyclophosphamide. They resume treatment with 3F8/GM-CSF if HAMA becomes negative.

9.3 3F8/GM-CSF treatment schedule (one cycle).

Days -5 to -1: GM-CSF 250 mcg/m²/day, subcutaneously.

Days 0 and +1: GM-CSF 250 mcg/m²/day, subcutaneously.
3F8 20 mg/m²/day by iv infusion over ~1.5 hr or less (usually 0.5 hr).

Days +2 to +4: GM-CSF 500 mcg/m²/day, subcutaneously.
3F8 20 mg/m²/day by iv infusion over ~1.5 hr or less (usually 0.5 hr).

Note: The daily GM-CSF is not administered if the ANC is >20,000/ul. The ANC count from the previous treatment day will be used to determine whether GM-CSF will be administered or not. If HAMA develops, cycles are deferred until HAMA titer decreases to <1000 Elisa units/ml. Emla cream (lidocaine 2.5% and prilocaine 2.5%) can be used to prevent pain from GM-CSF shots.

9.4 Isotretinoin is administered at 160 mg/m²/d, divided into two doses, x14 days. This treatment can be repeated after a minimum rest period of 14 days, for a total of 6 cycles. It is not taken on the same days as 3F8. All patients receive a minimum of 2 cycles of 3F8/GM-CSF before starting isotretinoin (only to be started after cycle 1 if HAMA develops and precludes timely administration of cycle 2).

10.1 EVALUATION DURING TREATMENT/INTERVENTION (TABLE 4)

Note: If for any reason tests cannot be completed on day 0, they will be completed on day 1

10.2 CBC on days 0 and +3 (Mondays and Thursdays). If ANC is >10,000/ul, CBC is repeated on next day.

10.3 C3 and CH50 on days 0 and +4 (Monday and Friday) of each cycle.

10.4 HAMA is approximately every 1-2 months while on study ([name], Research Lab).

10.5 Liver and kidney function blood tests on days 0 and +4 of each cycle.

10.6 BM studies (section 8.6) at end of cycles 2 and 4 and after the 6th cycle of Accutane. Subsequently, BM studies are repeated in conjunction with MIBG or PET scan (section 10.8) through 2 years in patients with history of BM or cortical bone involvement, but are repeated ~every 6 months in other patients (e.g., patients who were stage 4 by virtue of metastases in distant lymph nodes).

10.7 CT or MRI of primary site approximately every 3 months through 1 year.

10.8 ^{99m}Tc-MDP-bone scan approximately every 3 months while on study until normal.

10.9 MIBG or PET scan approximately every 3 months through 2 years.^{92,93}

10.10 Urine catecholamine levels approximately every 3 months through 2 years.

10.11 Pregnancy screen (females of child-bearing age) before starting *cis*-retinoic acid.

11.1 TOXICITIES/SIDE EFFECTS

11.2 Toxicities are graded by the Common Toxicity Criteria (Version 2.0) developed by the National Cancer Institute (NCI) of the USA.

11.3 3F8: Reversible side-effects include pain, paresthesia, hypertension, hypotension, tachycardia, urticaria, fever, nausea, emesis, and rarely, diarrhea, serum sickness, hyponatremia, somnolence and posterior reversible encephalopathy syndrome (PRES). Other potential side-effects that may occur are bronchospasm, anaphylaxis, peripheral neuropathy, impaired accommodation of the eye, and poor reactivity of pupils to light.

11.4 GM-CSF: Common side-effects include bone pain, flushing, local reaction at site of injection, leukopenia shortly after injection, and decrease in platelet count.⁹⁸ Rare side-effects (predominantly in adults) include allergic reactions, weight gain, pleural or pericardial effusion, pericardial embolism, thrombosis, and difficulty breathing after first injection.

11.5 Isotretinoin: Dry skin, cheilitis, dry eyes, hypercalcemia, pseudotumor cerebri, hepatotoxicity, teratogenic effect on fetus, depression, suicidal ideation.

12.1 CRITERIA FOR THERAPEUTIC RESPONSE/OUTCOME ASSESSMENT

12.2 Response duration is calculated from first day of treatment with 3F8.

12.3 *Group 1* patients (i.e., patients treated for primary refractory disease) are considered a treatment failure under this protocol if progressive disease develops.

12.4 *Group 2* patients (i.e., patients in CR/VGPR) are considered a treatment failure under this protocol if progressive disease develops.

12.5 Disease status is defined by the International Neuroblastoma Response Criteria,⁹¹ supplemented by RT-PCR findings in bone marrow (section 8.6)

- Complete response/remission (CR): no evidence of disease.
- Very good partial response/remission (VGPR): >90% decrease in all disease parameters, except bone scan unchanged or improved; bone marrow must be free of disease.
- Partial response/remission: >50% decrease in all disease parameters, except bone scan unchanged or improved; no more than 1 positive bone marrow site.
- Mixed response: >50% decrease in ≥ 1 but not all disease markers.
- Stable disease: <50% decrease in all tumor markers.
- Progressive disease: new lesion, or >25 % increase in any disease marker.

12.6 Adequacy of trial: All patients who fulfill the eligibility requirements and receive a first dose of 3F8 will have an adequate trial.

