2.1 OBJECTIVES AND SCIENTIFIC AIMS

- Assess the efficacy of subcutaneous GM-CSF in enhancing 3F8-mediated ablation of BM disease.
- Apply real-time quantitative RT-PCR to test the hypothesis that minimal residual disease content of BM after the first treatments with 3F8/GM-CSF has significant prognostic impact on relapse-free survival.
- Simplify treatment with consequent reduction in cost.

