advantageous for immune-based attack against cancer.²³ We and others have shown that Mac-1 (CD11b/CD18), FcRII, and FcRIII are required for optimal ADCC in a system using human PMNs as effectors, human NB cells as targets, and clinically active anti-GD2 MoAbs as mediators.^{35,36} Efficient tumor-cell kill occurs despite the large size of the targets (which precludes a role for phagocytosis) and their relative resistance to reactive oxygen species.⁴¹ GM-CSF enhancement of ADCC in this system correlates with upregulation of Mac-1 and with increased exocytosis of azurophil (primary) granules which contain cathepsin G and defensins capable of lysing NB cells.⁴² To elucidate the cytotoxic mechanisms of anti-GD2 MoAb-mediated ADCC, we used blocking MoAbs, PMNs devoid of Mac-1 (from donors with leukocyte adhesion deficiency), and PMNs that do not generate reactive oxygen species (from donors with chronic granulomatous disease),³⁵ while others used blocking MoAbs, electron microscopy, and PMNs from healthy donors as well as from patients.³⁶

3.7 Rationale for quantitating BM disease by real-time RT-PCR: Curative strategies for stage 4 NB must encompass control of both the primary mass and distant disease. Dose-intensive chemotherapy has had a favorable impact on resectability of primary tumors and surgical removal of all visible tumor, followed by local radiotherapy, reduces the risk of relapse in the primary site to <10%.^{4,7} Dose-intensive chemotherapy eliminates histologically evident BM involvement in 90% of high-risk cases.³ These encouraging results have shifted the focus of curative strategies to the problem of MRD – which is readily assessed in BM.

Adjuvant treatments, such as immunotherapy with monoclonal antibodies, may make gradual and not quantum changes in MRD, which by definition is beyond the sensitivity of conventional histologic⁵⁸ or radiographic techniques. The availability of more sensitive methods for identifying and quantitating occult tumor cells in sequential BM specimens can allow determination of the efficacy and optimal duration of adjuvant treatment. Thus, the absence of detectable tumor cells in BM can serve as a surrogate end point for the adjuvant treatment strategy, while quantitative data on BM disease will help detect relapse earlier and indicate a need for a change in treatment.

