subjects, 18 will be accrued during stage 1 and 15 during stage 2. The trial stops early if none of the first 18 patients survive for two years without relapse. Otherwise, the trial continues until 33 patients are accrued. Treatment will be considered promising if two or more patients experience two-year relapse-free survival and accrual can continue up to 50 patients with the goal of strengthening the findings

* Patients with prior antibody treatment or immunotherapy are less common and so only a trial with lower power is feasible. We will accrue 19 patients, declaring treatment as promising if two or more experience two-year relapse-free survival. This design has a power of 80% and an alpha of 5%, a null hypothesis of 1% and an alternate hypothesis of 15%. Only a one-stage design is feasible with these characteristics as an observed zero response rate would be consistent with a true response rate of 15% for an interim analysis conducted at all possible stopping points up to the 18th patient. If the findings are favorable, accrual can increase to 35, with the aim of strengthening the conclusions.

* Patients who went off protocol to receive therapy for relapse in the central nervous system, or to receive additional chemotherapy because of HAMA (section 9.1), are not included in the statistical analyses for these groups.

Utility of RT-PCR: The association between histologic examination and real time RT-PCR regarding BM status can be assessed by the Wilcoxon statistic. The clinical significance (relapse-free survival) of histologic results and real time RT-PCR findings in both groups can be assessed by log-rank test or Cox regression model or time dependent Cox regression model.

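### Marrow RT-PCR is part of the disease-status definition and is also the predictor tested against relapse-free survival; nothing keeps it out of the event, so the prognostic analysis may be partly circular and the two-year endpoint may lose power

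*Combined protocol and SAP*

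**What the plan says.** **Outcome.** Section 12.5 takes disease status from the International Neuroblastoma Response Criteria, "supplemented by RT-PCR findings in bone marrow (section 8.6". Its last entry reads "Progressive disease: new lesion, or >25 % increase in any disease marker". Under 12.3 and 12.4, patients in either group "are considered a treatment failure under this protocol if progressive disease develops". Section 14.0 uses two-year relapse-free survival for its decision rules, and names marrow CR as the Group 1 response endpoint, without defining relapse separately.

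**Predictor.** The second objective in section 2.1 is to test whether "minimal residual disease content of BM after the first treatments with 3F8/GM-CSF has significant prognostic impact on relapse-free survival". Section 14.0 (Utility of RT-PCR) adds: "The clinical significance (relapse-free survival) of histologic results and real time RT-PCR findings in both groups can be assessed by log-rank test", or by a Cox or time-dependent Cox model.

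**Intended role of the assay.** Section 3.7 expects that "quantitative data on BM disease will help detect relapse earlier and indicate a need for a change in treatment".

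**Missing rule.** No RT-PCR threshold for response or progression is given. The cut-off of 5 for a negative transcript appears only under the historical tables in 3.8. Section 8.6, which 12.5 cites for the RT-PCR findings, lists histochemistry and immunocytology but not RT-PCR. Table 4 does mention RT-PCR among the marrow studies.

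**The concern.** A prognostic analysis needs an outcome that is determined without the predictor. Here one assay sits on both sides and no sentence separates them. If some patients are called progressive because their transcript persists or rises, RT-PCR-positive patients will show worse relapse-free survival for that reason alone. The exposure is greatest if persistent positivity is treated as progression, or if serial RT-PCR values enter the time-dependent Cox model, because the covariate and the event could then come from the same marrow sample.

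The decision rules are also exposed. The 13% and 55% benchmarks come from the predecessor trial. Section 3.8 describes the RT-PCR work in patients given iv GM-CSF as retrospective, and 3.9 reports marrow CR by histology. If the new trial counts RT-PCR-only events and the benchmark did not, the comparison is not like for like. The event definition behind the benchmarks is not given, so this is an inference.

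**Working it through.** The documents give no rate of RT-PCR-only progression, so the sizes below use assumed rates.

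**1. Reproduce the Group 2 design.** Inputs from section 14.0: p0 = 0.55, type I error 0.05, power 0.85, N = 75, success if at least 49 are relapse-free. The promising rate is printed as 1.70, which cannot be a probability. I read it as 0.70 because that reproduces N.

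One-sided normal formula: N = [(z_α√(p0(1−p0)) + z_β√(p1(1−p1))) / (p1−p0)]²
= [(1.645 × 0.4975 + 1.036 × 0.4583) / 0.15]² = 74.3, so 75.

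Exact binomial: P(X ≥ 49 | 75, 0.55) = 0.045 and P(X ≥ 49 | 75, 0.70) = 0.843. The design reproduces.

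**2. Effect of RT-PCR-only events on that rule.** Let d be the share of patients relapse-free by standard criteria who are called progressive on RT-PCR alone by two years. The observed rates become p0(1−d) and p1(1−d), and the rule stays at 49 of 75. At p1 = 0.70, 75 × 0.70 = 52.5 patients are expected relapse-free, so the number reclassified is 52.5d.

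| d | Reclassified (of 52.5) | Observed p1 | Type I error | Power |
|---|---|---|---|---|
| 0 | 0 | 0.700 | 0.045 | 0.843 |
| 2% | 1.1 | 0.686 | 0.030 | 0.771 |
| 5% | 2.6 | 0.665 | 0.015 | 0.636 |
| 10% | 5.3 | 0.630 | 0.004 | 0.386 |

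Type I error falls along with power, so the bias is against the treatment. A relapse that RT-PCR only brings forward within the two years leaves the two-year count unchanged. Only calls that would otherwise fall later, or never, enter d.

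In Group 1, at the stated rule of 12 of 70, power falls from 0.956 to 0.930 at d = 5% and 0.891 at d = 10%. That rule has an exact type I error of 0.193, not the stated 0.05. This is a separate matter and makes Group 1 the less useful illustration.

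**3. Effect on the prognostic test.** Assumptions:
- 75 patients, 32% RT-PCR positive. This is the pretreatment figure for first CR/VGPR in Table 1, used as a stand-in for early post-treatment positivity. It gives 24 positive and 51 negative.
- True two-year relapse-free survival of 0.55 in both marker groups, so there is no prognostic effect.
- A share e of event-free positive patients called progressive on RT-PCR alone. Their observed rate becomes 0.55(1−e), and the number reclassified is 24 × 0.55 × e = 13.2e.
- A two-sided 5% pooled test of two proportions.

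| e | Reclassified | Observed rate, positive vs negative | False prognostic finding |
|---|---|---|---|
| 0 | 0 | 0.55 vs 0.55 | about 5% |
| 20% | 2.6 | 0.44 vs 0.55 | about 14% |
| 30% | 4.0 | 0.385 vs 0.55 | about 26% |
| 50% | 6.6 | 0.275 vs 0.55 | about 62% |

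**The case against.** The strongest reply is that the harm depends on how one word, supplemented, is applied. The protocol never says that a transcript rise alone is progression or relapse, and several passages point the other way. Section 1.0 defines Group 2 as having no disease on standard studies. Section 3.9 reports historical marrow CR by histology. The road maps in 4.3 name RT-PCR and histology separately. Section 3.12 treats the assay's sensitivity as still to be shown. All of this stands, and it is why the point says may.

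Four stronger inferences are tempting, and the documents do not support them.

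- *The second objective would be met by construction.* The exposure in 2.1 is an early marrow level, not a later rise. Assay noise alone does not link the two. With assumed log-normal noise of CV 15% or 40% in stable patients, the chance that one of three later samples exceeds baseline by more than 25% is the same after a high or a low first follow-up value: 30% in both, or 58% in both. Circularity needs persistent positivity to be called an event, or serial values in the model.
- *Table 3 shows how often the 25% trigger would fire.* The non-responder rise from 139.0 to 312.4 is a ratio of group means, not a per-patient rate. From Table 2, the 30 non-responders are 8 + 7 + 5 + 10, and the 10 had progressive disease, which section 6.3 excludes here.
- *About a third of Group 2 would lose CR status.* Table 1 lists its 32% RT-PCR-positive patients as first CR/VGPR, so positivity did not remove that status.
- *The endpoint has drifted from its benchmark.* Without the benchmark's event definition, drift can be neither shown nor sized.

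**Conclusion.** The concern holds in conditional form. The text puts RT-PCR into disease status, makes an increase in any disease marker progression, makes progression the failure event, and then tests RT-PCR against relapse-free survival. No sentence keeps the assay out of the event, and section 3.7 gives an investigator reason to use it to call relapse. The prognostic result may therefore be partly circular.

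The two-year comparison may also lose power, and small numbers matter. Between two and three reclassified patients in a Group 2 cohort of 75 take power from 0.84 to 0.64, and about four reclassified positive patients take the false prognostic rate from 5% to about 26%. These figures rest on assumed reclassification rates, on 0.70 for the printed 1.70, and on 32% positivity as a stand-in. They show sensitivity and do not predict what the trial will find. The bias on the decision rules cannot produce a false claim that the treatment is promising.

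**What to change.** 1. In 12.5 and 14.0, state that for the section 14.0 endpoints (marrow CR and two-year relapse-free survival) response, progression and relapse are classified by the international criteria without RT-PCR. For these analyses, a patient with a molecular-only rise stays relapse-free until those criteria are met.
2. Define two-year relapse-free survival on the same criteria as the predecessor benchmark, and state what those criteria were.
3. Report molecular response separately, with its threshold. Any endpoint that counts RT-PCR-based events can be a sensitivity analysis.
4. Test RT-PCR from a fixed early sample as a landmark predictor of the RT-PCR-free endpoint. The end of cycle 2 is already a marrow assessment in both road maps, Table 4 and 10.6. Patients with an event before the landmark are counted and left out of that test.
5. Reconcile the reference in 12.5 with section 8.6, which does not list RT-PCR.

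The cost is about one sentence in each of 12.5 and 14.0, plus the corrected cross-reference. No extra samples or patients are needed. The small downside is that molecular-only relapse is reported beside the endpoint and not as an event. The change concerns classification for analysis only and does not bear on when treatment stops.
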